## Study Timeline

Milestones	Estimated Timelines (# months)
Contracting	1 month
IRB Approval	1 month
First Patient, First Visit (FPFV) date or Data Collection start date	1 month after IRB
Last Patient, Last Visit (LPLV) date or Data Analysis start date	4 months after FPFV
Final Clinical Study Report (CSR)	2 months after LPLV

## Share of Voice (SoV) Plan

	Target Congress	Target Presentation Date
Abstract in Congress	AOA/AAOpt	2027

	Target Journal	Target Submission Date
Manuscript	Contact Lens and Anterior Eye (CLAE) / Clinical Optometry	2027

## Recruitment

Participants will be recruited using IRB-approved recruitment materials, including flyers and digital advertisements. Recruitment flyers will be posted in co-managing clinic locations and shared via electronic methods, including email distribution and social media platforms associated with the study site.

In addition, the study team will identify potential participants through review of the clinic's existing patient database. This review will be limited to patients who have previously been fitted with Infuse Multifocal Contact Lenses and who may meet preliminary eligibility criteria. Only authorized study personnel will access this information for recruitment purposes.

Identified patients may be contacted by phone, email, or other HIPAA-compliant methods to inform them about the study and assess interest in participation. Initial contact will be limited to providing general study information, and no study procedures will be conducted prior to obtaining informed consent.

Interested individuals will be instructed to contact the study team using the information provided or may choose to respond directly to outreach. All recruitment materials and methods will be IRB-approved prior to use, and no coercive or misleading language will be included.

## Consent and Screening

All participants will undergo an informed consent process prior to the initiation of any study-related procedures.

Potential participants will not be provided with the informed consent form (ICF) prior to Visit 1. The informed consent process will take place on-site at the study visit. At that time, participants will be given sufficient time to review the ICF, ask questions, and discuss participation with study staff prior to signing. Written informed consent will be obtained before any study-specific procedures are performed.

Screening procedures will occur after informed consent is obtained and will include review of medical and ocular history, as well as any necessary clinical assessments to confirm eligibility. Eligibility will be determined based on the Inclusion and Exclusion Criteria outlined in the protocol. Only participants who meet all eligibility criteria will be enrolled in the study.

## Early Withdrawal of Subjects

Participants may be withdrawn from the study prior to completion for the following reasons:

- Voluntary withdrawal of consent at any time
- Occurrence of adverse events or safety concerns
- Failure to comply with study procedures or protocol requirements
- Investigator determination that continued participation is not in the participant's best interest

In the event of early withdrawal or study termination, participants may be asked to return any unused study materials, including contact lenses, if applicable. The reason for withdrawal will be documented when available.

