##### Visit 2 – Week 1 Follow-up visit (1 week after V1)

- Patient will follow up at 1 week in case power adjustment is needed, as determined by the PI

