## **Study Considerations:**

### **1. Longitudinal Baseline Control**

Consideration: Baseline assessments (Visit 1) must be performed while the subject is wearing their habitual Infuse Multifocal lenses to capture a "satisfied" state of ocular comfort and visual acuity before the intervention.

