### Primary Endpoint:

- The proportion of participants with CLDEQ-8 <12 after 2-weeks of wearing DAILIES TOTAL1 Multifocal (w finalized prescription)

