## Inclusion & Exclusion Criteria

### Inclusion Criteria:

- Age  $\geq 40$  years at the time of enrollment.
- Current satisfied wearer of Bausch + Lomb Infuse One-Day Multifocal (kalifilcon A) contact lenses in both eyes, CLDEQ-8  $< 12$  at baseline.
- Minimum wearing time of at least 8 hours per day, at least 5 days per week, for a minimum of 30 days prior to Visit 1.
- Best-corrected distance visual acuity (BCDVA) of at least 20/25 (0.18 LogMAR) or better in each eye.
- Manifest refraction within the parameters of the study lenses (e.g., Sphere: +6.00D to -10.00D; Add: Low, Med, High).
- Willingness to adhere to the study protocol, including the use of DAILIES TOTAL1 (DT1) Multifocal lenses for 8 hours per day, at least 5 days per week, and completion of all questionnaires (e.g. CLDEQ-8, SANDE, WPAI-SHP, VAS and other Likert question items).
- Ability to provide written informed consent and follow investigator instructions

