## Sample Size Justification

Target enrollment: 30 participants. This will be a prospective study to understand if satisfied Infuse Multifocal CL wearers can be successfully refit into Dailies Total1 Multifocal CLs. The Primary Endpoint will be simply analyzed as the proportion of subjects who have CLDEQ-8 scores  $<12$  at the end of the study. We estimate that 30 completed subjects will be enough to gain a general understanding of CL success and patient reported outcomes based upon past research (Duong et al., 2021a; Duong et al., 2021b). A sample size of  $N=30$  would satisfy the requirements of the Central Limit Theorem, ensuring the normality of the sampling distribution for parametric testing. Thus, 33 subjects can be recruited, so if a subject drops out before completing the study, they will be replaced.

The study is exploratory and not powered as a confirmatory superiority trial.

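### Short wear of the study lens can be treated as non-compliance, so a participant who cuts wear for discomfort may be withdrawn and replaced before the only CLDEQ-8 on that lens

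*Protocol*

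**What the plan says.** Four parts of the protocol bear on this. No SAP was available.

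- **Early Withdrawal of Subjects.** The list opens with "Participants may be withdrawn from the study prior to completion for the following reasons" and includes "Failure to comply with study procedures or protocol requirements". It makes no exception for non-compliance caused by the lens. At withdrawal it provides for possible return of unused lenses and a documented reason, but for no questionnaire.
- **Inclusion Criteria.** One criterion is "Willingness to adhere to the study protocol", which is spelled out as "including the use of DAILIES TOTAL1 (DT1) Multifocal lenses for 8 hours per day, at least 5 days per week".
- **Visit schedule and Study Assessments table.** CLDEQ-8 is taken at Visit 1 and Visit 3 only. The Visit 1 score belongs to the old lens: "Baseline assessments (Visit 1) must be performed while the subject is wearing their habitual Infuse Multifocal lenses". Visit 2 has no CLDEQ-8. Its stated purpose is "Patient will follow up at 1 week in case power adjustment is needed, as determined by the PI", and the table adds a safety assessment.
- **Sample Size Justification.** The study rests on 30 completers and allows 33 recruits, and "if a subject drops out before completing the study, they will be replaced".

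The primary endpoint is the proportion scoring below 12 on CLDEQ-8 after two weeks on the finalised DT1MF prescription. It is reported with an exact 95% interval. The Study Hypothesis names 70% or more.

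**The concern.** Wearing a lens for fewer hours, or leaving it out on some days, is an ordinary response to discomfort or unstable vision. CLDEQ-8 measures those same things, and its last item asks how often the wearer felt a need to stop and remove the lenses. The behaviour that signals a poor outcome can thus also serve as a ground for removal before that outcome is recorded.

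Three features make this matter. The investigator who decides is unmasked, because the study is open-label. There is one arm, so no comparator shares any distortion. A removed participant is replaced, so the final count of 30 would not show that anyone was lost.

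The point is about people who would still attend Visit 3. How voluntary dropouts are counted is a separate question. An SAP can say how a missing answer is treated, but it cannot recover an answer that was never collected.

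**Working it through.** **1. Is each link in the text?**

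| Link | Where | What it supports |
|---|---|---|
| Non-compliance is a ground for withdrawal | Early Withdrawal of Subjects | Permitted, not mandatory |
| Wear schedule is part of adherence | Inclusion Criteria | Named within a willingness criterion; no on-study threshold |
| One CLDEQ-8 on DT1MF | Visit 3 procedures; Study Assessments | Removal before Visit 3 ends outcome collection |
| No questionnaire at exit | Early Withdrawal of Subjects | Nothing replaces the lost score |
| Dropouts replaced | Sample Size Justification | Denominator refilled to 30 |

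**2. The plan's own numbers.** Spare places = 33 − 30 = 3, which is 3/33 = 9.1% of recruits. No dropout rate is stated, and 30 is not derived from a power or precision formula, so there is no further figure to reproduce.

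**3. Form of the bias.** Let p be the success rate among those kept, q the success rate the removed participants would have had, and w the share removed.

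Overstatement = p − [(1 − w)p + wq] = w(p − q).

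It is positive if q < p, zero if q = p and negative if q > p. The protocol gives neither w nor q.

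**4. Illustration.** Assume that all 33 are dispensed lenses, that all three spare places replace participants withdrawn for short wear, and that all three would have scored 12 or more (w = 3/33, q = 0). Intervals are exact Clopper–Pearson 95%.

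| Reported | Among all 33 | Overstatement (points) | At or above 70%? |
|---|---|---|---|
| 21/30 = 70.0% (50.6–85.3) | 21/33 = 63.6% (45.1–79.6) | 6.4 | yes → no |
| 22/30 = 73.3% (54.1–87.7) | 22/33 = 66.7% (48.2–82.0) | 6.7 | yes → no |
| 23/30 = 76.7% (57.7–90.1) | 23/33 = 69.7% (51.3–84.4) | 7.0 | yes → no |
| 24/30 = 80.0% (61.4–92.3) | 24/33 = 72.7% (54.5–86.7) | 7.3 | yes → yes |

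Check by the formula at 23/30: (3/33) × (23/30 − 0) = 0.0909 × 0.7667 = 0.0697, or 7.0 points.

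**5. Sensitivity to q.** Take 23/30 again and let some of the three removed participants be successes:

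- one of three: 24/33 = 72.7%
- two of three: 25/33 = 75.8%
- all three: 26/33 = 78.8%, above the reported 76.7%

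**6. Effect on the chance of reaching 21/30.** Assume a true success rate of 65%, and that a fraction r of would-be failures is removed and replaced from the same population under the same practice. The expected reported proportion is 0.65 / [0.65 + 0.35(1 − r)].

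- r = 0: 65.0%; chance of at least 21/30 is 36%.
- r = 10%: 0.65/0.965 = 67.4%; chance 46%.
- r = 25%: 0.65/0.9125 = 71.2%; chance 65%. The share removed is 0.35 × 0.25 = 8.75%, about 3 of 33.

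The 65% and both values of r are assumptions.

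**The case against.** The case against is substantial, and much of it stands.

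- **Withdrawal is discretionary.** A reader might infer that short wear leads to removal by rule. The text says only that participants may be withdrawn.
- **No wear threshold exists.** A reader might infer that falling below 8 hours or 5 days triggers withdrawal. The schedule appears once, inside an enrolment criterion on willingness. No section sets a cut-off or schedules a wear-time measurement.
- **The route is narrow.** Visit 2 is the only scheduled contact before Visit 3, and it exists to adjust power, which is a response to a poor fit. CLDEQ-8 is listed first at Visit 3. Removal would have to occur at Visit 2 or between visits.
- **The direction is not certain.** The CLDEQ-8 intensity items refer to the end of wearing time, so shorter wear may lower the score. Some people cut wear for unrelated reasons.
- **The consequence is limited.** The study is described as exploratory, no test against 70% is stated, and the paired intervals overlap almost entirely. The illustration also leaves no spare place for ordinary dropouts.
- **Real-world validity.** A reader might infer a conflict with the protocol's stated wish to preserve it. That phrase only explains why there is no washout and says nothing on wear or withdrawal.

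What these points leave standing is that the text allows the removal, offers no safeguard and collects nothing afterwards. Discretion held by an unmasked investigator makes selective removal harder for a reader to check. Denominators and scoring may sit in an SAP, but whether the Visit 3 answer is collected is a protocol matter.

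**Conclusion.** The concern holds as a permitted, avoidable route to upward bias in the primary proportion. It does not hold as a bias built in by rule. The upward direction rests on the assumption that participants withdrawn for short wear would score below 12 less often than those kept. That is plausible when discomfort or poor vision is the cause, but the documents do not establish it.

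The size is unknown. If all three spare places went to would-be failures, the overstatement would be 6.4 to 7.3 points for reported counts of 21 to 24 out of 30. This would take 21, 22 or 23 successes below 70% but not 24. A reader might infer that the trial's result will be inflated by about this much, or that its hypothesis would fail. The documents support neither, since every removal and failure rate used here is assumed. The change is worth making because the lost answers cannot be recovered later and the cost is small.

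**What to change.** In Early Withdrawal of Subjects, state that reduced or stopped DT1MF wear is not by itself a reason to end data collection or to replace the participant. Align the replacement sentence in Sample Size Justification. Clinical reasons for stopping lens wear are left unchanged.

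Unless they withdraw consent, these participants complete the Visit 3 questionnaires at the planned date. Record actual DT1MF wear time (hours per day, days per week), any other lens worn, and the reason for reduced wear.

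They stay in the primary denominator, with scoring fixed in advance in the protocol or SAP:

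- Those still mainly wearing DT1MF are scored by their Visit 3 CLDEQ-8.
- Those who stopped DT1MF, or went back mainly to another lens, because of comfort or vision count as not below 12. This avoids crediting DT1MF with a good score earned mostly in another lens.
- Those who stopped for unrelated reasons are reported separately, and their status is varied in a sensitivity analysis.

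Show a result in those who met the wear schedule beside the primary one.

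Cost: a short addition to the withdrawal text, an aligned replacement sentence and two or three extra Visit 3 fields. No visit, procedure or participant is added. The small downside is that some scores will come from people with reduced wear, which the result in those who met the schedule puts in context.

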## **Risks**

In addition to other study-related risks, participants undergoing corneal fluorescein staining with sodium fluorescein may experience:

- Mild, brief stinging or irritation upon instillation
- Temporary blurred vision immediately following application
- Rarely, allergic reactions such as itching, redness, or swelling

These effects are typically transient and resolve without intervention.

## **Ethical Considerations**

This study will be conducted in accordance with:

- The approved study protocol
- Principles of Good Clinical Practice (GCP)
- Applicable federal, state, and local regulatory requirements
- Institutional Review Board (IRB) requirements and determinations

The rights, safety, and well-being of study participants will be the primary consideration throughout the study.

## **Study Supplies**

All contact lenses used in this study are FDA-approved medical devices and are not investigational. They will be used in accordance with their approved labeling.

## **Confidentiality**

All participant information will be kept confidential to the extent permitted by law. Data will be de-identified where possible and stored securely with access limited to authorized study personnel.

Participant information will not be sold to third parties.

De-identified data may be used for future research purposes without additional consent, in compliance with applicable regulations and IRB approval.

## **Compensation**

Participants will receive compensation for their time and participation in the study. Compensation will be provided as \$125 per completed study visit, for a total of up to \$375 for all three visits.

Compensation will be provided at the end of the participant's study involvement. If a participant withdraws early or does not complete all study visits, compensation will be prorated based on the number of visits completed and provided at the time of withdrawal or study termination. Compensation is not contingent upon completion of all study visits.

The method and timing of compensation will be described in the informed consent form.

### **Supply:**

- One (1) DT1mf fitting set.
- Study lenses in quantities sufficient to support conduct of the Study. For planning purposes only, total lens usage is currently estimated at up to approximately 4,500 single lenses ("30 subjects \* 2 eyes \* 25 minimum).

#### **1. Risks to Subject Privacy**

- a. There is a risk of loss of confidentiality of subject information. The site will take adequate measures to minimize this risk by safeguarding all documents associated with subject and the study and by using a unique, anonymized, subject identifying number for each subject.

#### **2. Potential Benefits of Participation**

- a. Subjects enrolled in this study may experience an improvement in the clinical signs and symptoms of their dry eye disease.

#### **3. Data Handling and Record Keeping**

- a. All personal and medical information collected from participants will be kept confidential and stored securely. Information will only be accessible to the study team members directly involved in the trial. Access to the study data will be restricted to authorized personnel only. The study team will have a designated file storage system where all data will be securely stored. Participants' identities will be kept anonymous and assigned a unique identification code. This code will be used to track their progress throughout the trial. Any data shared with external organizations or individuals will be de-identified to ensure that patient confidentiality is maintained.

#### **4. Source Documentation**

- a. The following documents are defined as source documents for this study:
  - i. Informed Consent Documentation
  - ii. Case Report Forms
  - iii. Medical Records
  - iv. Adverse Event Reports

#### **5. Records Retention**

- a. All study records will be retained for a minimum of 7 years after the completion of the study or termination of the study, in accordance with applicable regulatory requirements. The PI and the sponsor are responsible for ensuring that all study records are retained in accordance with this protocol. All study records will be stored securely in a locked cabinet or a password-protected electronic system to prevent unauthorized access or loss. Study records will be made available to regulatory authorities upon request, and the Sponsor and PI will retain access to the study records for the duration of the retention period. At the end of the retention period, study records will be destroyed in a manner that maintains participant confidentiality and privacy.
6. Study Monitoring, Auditing, and Inspection
- a. The study monitoring team will be composed of the PI and designated study staff. The team will be responsible for monitoring the study progress, identifying, and resolving issues, and reporting to the Institutional Review Board (IRB) and other regulatory authorities. The study monitoring team will review the study data on an ongoing basis to ensure accuracy, completeness, and timeliness. This will include reviewing case report forms (CRFs) and adverse event reports. The study monitoring team will monitor and review all adverse events reported during the study to ensure that they are being appropriately documented, reported, and managed. The study monitoring team will review all protocol deviations and violations to ensure that they are appropriately reported and managed. The study monitoring team will monitor compliance with the protocol, Good Clinical Practice (GCP) guidelines, and applicable regulations. This will include reviewing the Investigator Site File (ISF) and ensuring that all required study documentation is maintained and up to date. The study monitoring team will conduct quality control activities to ensure that the study is being conducted to the highest standards. This will include reviewing the study monitoring plan, SOPs, and other study-related documents. Regular reports will be provided to the PI, IRB, and other regulatory authorities as required.

## Study Budget

Clinical Study Budget for IIT #103124963 - Prospective Study

How does DT1 MF perform in satisfied Infuse One-Day MF wearers?

[name], OD

Number of Patients: 33  
 Currency: USD

Study Costs	Cost
Essential documentation prep (protocol, informed consent, CRF binding)	\$6,900.00
IRB/Ethics Committee	\$4,500.00
Biostatistics/Data Analysis	\$5,000.00
Close out	\$500.00
Medical Writing (manuscript/final report, abstracts, presentation prep)	\$16,100.00
Open Access Fee (based on journal fee)	\$4,500.00
Patient reimbursement (33 patients x \$375)	\$12,375.00
TOTAL SITE BUDGET	\$126,105.00

Per Patient Costs	Recruitment Visit	Follow-up visit 1	Follow-up visit 2	Total Cost
		Cost	Cost	
Study/Clinical Coordinator activity (informed consent, recruitment, retention, qualification verification)	\$250.00	\$75.00	\$200.00	\$525.00
Procedural Study Costs (VA, clinical evaluation, CL fit/assessment)	\$475.00	\$150.00	\$375.00	\$1,000.00
Procedural Study Costs (questionnaires, surveys)	\$150.00	\$0.00	\$150.00	\$300.00
IP Accountability	\$50.00	\$0.00	\$50.00	\$100.00
Total Per Patient Cost Incl. Reimbursement				\$1,925.00
	Institutional Overhead	20%		\$385.00
				\$2,310.00

## Appendix

**Please remind subjects that ratings are to be given based on their most recent pair of study lenses given**

### **VAS**

Comfort (0 poor to 100 excellent)

Overall vision (0 poor quality to 100 excellent quality)

Satisfaction (0 poor to 100 excellent)

## Likert questionnaires

Item	Responses (right to left)
How satisfied are you with the comfort these lenses provided?	Very satisfied Satisfied Neither satisfied nor dissatisfied Dissatisfied Very dissatisfied
How satisfied are you with your overall vision while wearing these lenses?	Very satisfied Satisfied Neither satisfied nor dissatisfied Dissatisfied Very dissatisfied
These lenses make it convenient for me to perform my daily activities.	Strongly agree Agree Neither agree nor disagree Disagree Strongly disagree
I'm likely to continue wearing these contact lens after the study ends	Strongly agree Agree Neither agree nor disagree Disagree Strongly disagree
I would recommend the study contact lenses to a family member or friend	Strongly Agree Agree Neither Agree nor Disagree Disagree Strongly Disagree

## CLDEQ-8

### CONTACT LENS QUESTIONNAIRE-8 (CLDEQ-8)

#### 1. Questions about EYE DISCOMFORT:

- a. During a typical day in the past 2 weeks, how often did your eyes feel discomfort while wearing your contact lenses?

- 0 Never
- 1 Rarely
- 2 Sometimes
- 3 Frequently
- 4 Constantly

When your eyes felt discomfort with your contact lenses, how intense was this feeling of discomfort...

- b. At the end of your wearing time?

Never have it	Not at All Intense				Very Intense
0	1	2	3	4	5

